 - At C1D1 and any visit when pembrolizumab and ASP0739 are administered together, ECGs are obtained predose (-1 h from start of pembrolizumab infusion) and 1 to 2 h post dose of ASP0739.
 - ASP0739 dosing only: ECGs are obtained predose (-1 h from start of ASP0739 infusion) and 1 to 2 h post dose of ASP0739.
 - Pembrolizumab dosing only: ECGs are obtained predose (-1 h from start of pembrolizumab infusion) and 1 to 2 h post dose of pembrolizumab.
- k. Includes medications taken within 28 days prior to C1D1. Include all anticancer treatment received 28 days prior to IP administration.
- l. Urine or serum pregnancy test will be performed in women of childbearing potential. On treatment visit days, test must occur prior to IP administration.
- m. Laboratory tests will be analyzed by the institution's local laboratory. However, sample results must also be submitted for centralized data entry. Laboratory test may be repeated during the screening period. For participants in combination therapy arm, troponin levels will be obtained at screening; thereafter, weekly for 6 weeks and subsequently every second week for 6 weeks.
- n. Thyroid panel including triiodothyronine or free triiodothyronine, free thyroxine and thyroid stimulating hormone will be measured prior to receiving pembrolizumab only for participants in the combination cohort (Screening, C2D15 then every 6 weeks).
- o. Whole blood for optional PGx study may be collected at C1D1 prior to IP administration.
- p. See [Table 5](#) for collection schedule for ASP0739 single agent and ASP0739 and pembrolizumab combination therapy.
- q. Archival tumor specimen at a minimum of 1 FFPE tumor tissue block with adequate viable tumor cells (preferred) OR a minimum of 20 FFPE unstained serial slides are required.
- r. Same technique (CT/MRI) used at screening should be utilized throughout the study. Imaging should include chest, abdomen and pelvis, as well as any other anatomical region appropriate for the participant's disease. Scans performed prior to informed consent as standard of care are acceptable as screening scans, if done within 28 days prior to C1D1. Imaging will occur every 56 ± 7 days until confirmed progression by iRECIST.
- s. Enrollment or randomization will be done via IRT system after confirmation of eligibility and prior to dosing.

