m. Laboratory tests will be analyzed by the institution's local laboratory. However, sample results must also be submitted for centralized data entry. Laboratory test may be repeated during the screening period. For participants in combination therapy arm, troponin levels will be obtained at screening; thereafter, weekly for 6 weeks and subsequently every second week for 6 weeks.

n. Thyroid panel including triiodothyronine or free triiodothyronine, free thyroxine and thyroid stimulating hormone will be measured prior to receiving pembrolizumab for participants in the combination cohort (Screening, C2D15 then every 6 weeks).

o. Whole blood for optional PGx study may be collected at C1D1 prior to IP administration.

p. See [Table 5](#) for collection schedule for ASP0739 single agent and ASP0739 and pembrolizumab combination therapy.

q. Archival tumor specimen at a minimum of 1 FFPE tumor tissue block with adequate viable tumor cells (preferred) OR a minimum of 20 FFPE unstained serial slides are required.

r. Same technique (CT/MRI) used at screening should be utilized throughout the study. Imaging should include chest, abdomen and pelvis, as well as any other anatomical region appropriate for the participant's disease. Scans performed prior to informed consent as standard of care are acceptable as screening scans, if done within 28 days prior to C1D1. Imaging will occur every 56 ± 7 days until confirmed progression by iRECIST.

s. Participants in all expansion cohorts are required to provide a tumor specimen obtained within 56 days prior to first dose of IP.

t. Participants in all expansion cohorts are required to provide an on-treatment tumor specimen collected ± 7 days of the C2D15 visit (or unscheduled).

u. The EOT visit will occur within 7 days of the principal investigator decision to discontinue the participant for treatment or prior to the start of new anticancer treatment, whichever occurs first. If a participant is completing all visits in the last treatment cycle, the EOT visit will be within 7 days from the last planned visit.

v. Samples collected at pembrolizumab doses 5, 7, 9, 11 and 13 only.

w. Samples collected at pembrolizumab doses 5 and 7 only.

x. Sample collected at the time of discontinuation due to disease progression.

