5.1 Inclusion Criteria

Participant is eligible for participation in the study if all of the following apply:

1. Institutional Review Board (IRB)/Independent Ethics Committee (IEC) approved written informed consent and privacy language as per national regulations (e.g., Health Insurance Portability and Accountability Act authorization for US study sites) must be obtained from the participant or legally authorized representative prior to any study-related procedures (including withdrawal of prohibited medication, if applicable).
2. Participant is at least 18 years of age and legally an adult according to local regulation at the time of signing the ICF.
3. Phase 1 Dose Escalation only:
 - Participant has R/R solid tumor known to express NY-ESO-1 (examples are, but not limited to, gastric cancer, melanoma, ESCC, NSCLC, MRCL, SS, hepatic, SCCHN or ovarian cancer) after completing available SOC therapy or is not a candidate for SOC therapy. NY-ESO-1 expression status is not required for participant entry.
4. Safety lead-in, Phase 2 Single agent and Combination Therapy only:
 - Participant has R/R SS or MRCL disease after undergoing available SOC treatment or is not a candidate for SOC therapy (must have previously received either an anthracycline or ifosfamide containing regimen or another systemic regimen, if not a candidate for either agent).
 - Participant has not received prior checkpoint inhibitor therapy (i.e., PD-1/PD-L1 treatment naïve)
 - SS: confirmation by the presence of a translocation between SYT on the X chromosome and SSX1, SSX2 or, SSX4 on chromosome 18 (may be presented in the pathology report as t [X; 18]). If unconfirmed, enrollment into the study should be discussed with the medical monitor.

- MRCL: confirmation by the presence of the reciprocal chromosomal translocation t (12;16) (q13;p11) or t(12; 22) (q13;q12). If unconfirmed, enrollment into the study should be discussed with the medical monitor.
- Participant has R/R ovarian cancer that is:
 - platinum resistant
 - OR
 - platinum-sensitive, but the participant is not a candidate for platinum or other SOC therapy.
 - Participant has not received prior checkpoint inhibitor therapy (i.e., naïve PD-1/PD-L1 treatment patients).
- Participant has R/R solid tumor (melanoma, NSCLC-adenocarcinoma and squamous cell or ESCC) after available SOC treatment or is not a candidate for SOC therapy (single-agent only).

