5.2 Exclusion Criteria

Participant will be excluded from participation in the study if any of the following apply:

1. Participant has persistent non-hematological toxicities of \geq grade 2 (NCI-CTCAE v5.0), with symptoms and objective findings from treatment (including chemotherapy, kinase inhibitors, immunotherapy, experimental agents, radiation or surgery).
2. Participant has received any of the following therapies (for inclusion in the study, all abnormalities must have returned to \leq grade 1):
 - Systemic immunomodulators (checkpoint inhibitors) - except the dose escalation phase and the NY-ESO-1 solid tumor (melanoma, NSCLC-adenocarcinoma and squamous cell and ESCC) cohorts in the dose expansion phase of monotherapy, which may have received prior checkpoint inhibitor therapy
 - Immunosuppressive drugs including steroids \leq 14 days prior to treatment
 - Cytotoxic agents \leq 14 days prior to treatment
 - Investigational agent \leq 21 days prior to treatment or 5 half-lives, whichever is shorter
 - Radiation therapy \leq 21 days prior to treatment
3. Participant has clinically active or untreated nervous system metastases. Participants with previously treated central nervous system (CNS) metastases are eligible, if they are clinically stable and have no evidence of CNS progression by imaging for at least 4 weeks prior to start of study treatment and are not requiring immunosuppressive doses of systemic steroids (> 30 mg per day of hydrocortisone or > 10 mg per day of prednisone or equivalent) for longer than 2 weeks.

4. Participant has an active autoimmune disease. Participant with type 1 diabetes mellitus, endocrinopathies stably maintained on appropriate replacement therapy, or skin disorders (e.g., vitiligo, psoriasis, or alopecia) not requiring systemic treatment are allowed.
5. Participant was discontinued from prior immunomodulatory therapy due to a grade ≥ 3 toxicity that was mechanistically related (e.g., immune related) to the agent in the judgment of the investigator.
6. Participant has known history of serious hypersensitivity reaction to a known ingredient of ASP0739 or pembrolizumab or severe hypersensitivity reaction to treatment with another monoclonal antibody.

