7.2.5 Imaging

Radiographic disease assessment is to be performed at screening and throughout the study every 56 ± 7 days. The same technique (CT/MRI) used at screening should be utilized throughout the study. Imaging should include chest, abdomen and pelvis, as well as any other anatomical region appropriate for the participant's disease. Scans performed prior to informed consent as SOC are acceptable as screening scans, if done within 28 days prior to C1D1.

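### The baseline scan is allowed to predate the last prior anticancer treatment, so shrinkage from that treatment can count as response to ASP0739

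*Protocol*

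**What the plan says.** **Scan rule.** Footnote r of Tables 1 and 2 reads: "Scans performed prior to informed consent as standard of care are acceptable as screening scans, if done within 28 days prior to C1D1". Footnote p of Tables 18 and 19 and Sections 7.1 and 7.2.5 repeat the rule; in 7.2.5 such scans "are acceptable as screening scans, if done within 28 days prior to C1D1". The condition is one of age only.

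**Prior-treatment rule.** Exclusion 2 (Protocol 5.2) lists:
- "Cytotoxic agents \leq 14 days prior to treatment"
- "Radiation therapy \leq 21 days prior to treatment"
- "Investigational agent \leq 21 days prior to treatment or 5 half-lives, whichever is shorter"

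Each interval runs back from study treatment. For checkpoint inhibitors, the dose escalation phase and the melanoma/NSCLC/ESCC monotherapy cohort are excepted as populations "which may have received prior checkpoint inhibitor therapy", with no interval stated. The SS and MRCL cohorts require: "Participant has not received prior checkpoint inhibitor therapy (i.e., PD-1/PD-L1 treatment naïve". The ovarian criterion is similar.

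**What is recorded.** Footnote k of Tables 1 and 2 says: "Include all anticancer treatment received 28 days prior to IP administration". It does not link that treatment to the scan date.

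**What baseline is.** Protocol 9.4.1 and SAP 6.1 take the last available value before the first dose, so an old scan stays the reference unless a later one is taken.

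**The concern.** Tumour response is change from the baseline scan. If another therapy acts between that scan and C1D1, its effect lies inside the measured change. Every phase 2 cohort is judged against a fixed rate rather than a concurrent control, so the error goes one way, toward apparent activity. Central review and a confirmatory scan at 4 weeks or more do not help, because the fault is in the reference scan.

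The affected quantities are iORR, ORR, iDCR, DCR and the spider and waterfall plots. Two enrolment decisions also rest on very few responses. One confirmed response in the melanoma/NSCLC/ESCC cohort allows a tumour-specific cohort to open, and two responses in a single-agent cohort allow the matching combination cohort to open (Protocol 4.1).

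**Working it through.** **1. Set the two rules side by side.** Take a scan on day -28, the oldest allowed.

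| Prior therapy | Latest day exclusion 2 permits | Days after the scan |
|---|---|---|
| Cytotoxic | -15 | 28 - 15 = 13 |
| Radiation | -22 | 28 - 22 = 6 |
| Investigational agent | -22, or later if 5 half-lives is shorter | at least 6 |
| Checkpoint inhibitor (dose escalation and melanoma/NSCLC/ESCC only) | no interval given | not bounded by exclusion 2 |

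These are the limits of exclusion 2 alone. Exclusion 2 also names no interval for approved agents that are neither cytotoxic nor immune-modulating.

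**2. Look for a rule that closes the gap.**
- Section 6.8 prohibits other cancer-directed therapy while on study. Screening is a listed study period (4.1), so a fair reading covers the time after consent. It cannot reach treatment given between a pre-consent scan and consent.
- Inclusion 17 closes the radiotherapy route only for a participant with a single measurable lesion.
- Inclusions 3 and 4 require relapsed or refractory disease, but not a scan taken after the last therapy.
- Section 7.1 asks for a repeat baseline scan, where possible, after biopsy of a target lesion. There is no counterpart after anticancer treatment.
- SAP 6.4 has no analysis directed at this.

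None of these closes it.

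**3. Reproduce the design's own error rate.** Single agent (Protocol 4.1 and 9.1): 18 participants, stop at 2 or fewer responses; otherwise continue to 43 and declare effective at 8 or more; null rate 10%, alternative 25%.

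P(pass | p) = sum over x from 3 to 18 of P(X1 = x) × P(X2 ≥ 8 - x), with X1 ~ Bin(18, p) and X2 ~ Bin(25, p).

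At p = 0.10 the terms for x = 3, 4, 5, 6, 7 and 8 or more are 0.0165 + 0.0165 + 0.0101 + 0.0038 + 0.0009 + 0.0002 = 0.048. At p = 0.25 the result is 0.800. Both agree with the stated 0.05 one-sided type I error and power of about 0.80 (9.2).

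**4. Add an assumed carry-over.** Let f be the share of non-responders scored as responders because of prior treatment. The documents give no value. The apparent null rate becomes 0.10 + 0.90 × f.

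| f (assumed) | Apparent rate | Type I error |
|---|---|---|
| 0 | 0.100 | 0.048 |
| 0.5% | 0.1045 | 0.059 |
| 1% | 0.109 | 0.072 |
| 2% | 0.118 | 0.103 |

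f is the share treated between scan and C1D1 multiplied by the share of those who then convert. For example, 5% × 10% = 0.5%, 10% × 10% = 1% and 20% × 10% = 2%.

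The combination designs behave similarly. At f = 1% and 2%, SS/MRCL goes from 0.042 to 0.058 and 0.079, and ovarian from 0.047 to 0.078 and 0.118.

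**The case against.** The strongest reply is that the gap is narrow and the numbers are hypothetical. Much of this stands.

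- **Length of the gap.** Because exclusion 2 sets no checkpoint-inhibitor interval, a reader might infer that one could be given up to day -1, 27 days after a day -28 scan. Section 6.8 does not support that. If it covers screening, treatment on day -1 would require consent and all screening to fit into about a day. The realistic exposure ends at consent.
- **Which cohorts.** A reader might also carry the checkpoint-inhibitor route into the error rates above. It cannot reach the SS, MRCL and ovarian cohorts, which must be treatment-naive to that class. The cohort that allows prior use has no formal hypothesis (9.1), and a response there only permits an expansion cohort to open.
- **Size.** Larger carry-over can be assumed: f = 5% gives a type I error of 0.23. But if only 5% of participants were treated in the gap, every one of them who would otherwise not respond would have to convert. The disease is relapsed or refractory, and the documents support no such rate.
- **Footnote k.** It is a recording instruction and does not show that treatment after the scan is expected.
- **Other mitigation.** Phase 2 requires a tumour specimen from within 56 days before dosing, so some participants may have a repeat scan under the biopsy rule. Not every biopsy is of a target lesion, and the repeat is only where possible. The imaging charter is not available here and might contain a baseline-selection rule.

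None of this supplies the missing requirement that the scan follow the last therapy.

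**Conclusion.** The concern holds as a gap between two rules: scan age and treatment-free interval are both counted from C1D1, and neither refers to the other. In the formally tested cohorts the routes are cytotoxics, investigational agents and, for participants with more than one measurable lesion, radiotherapy. In dose escalation and the melanoma/NSCLC/ESCC cohort, checkpoint inhibitors are added.

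The size is unknown. The single-agent design has little slack, since an assumed f of 0.5% already takes it past 0.05. That shows sensitivity; it does not estimate actual bias.

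The SAP (Section 1) reports early termination, no combination treatment and no central review, so the type I error figures now only illustrate the design. What remains is descriptive, investigator-assessed response in small groups. Four participants had been treated as of 06 May 2022 (Protocol 2.3.1.1); in a group of that size, a single carry-over response would alone give 1/4 = 25%.

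**What to change.** 1. **Protocol.** In six places (Table 1 and Table 2 footnotes r, Table 18 and Table 19 footnotes p, Sections 7.1 and 7.2.5), state that the baseline scan must be taken after the last dose of any prior anticancer therapy, including radiotherapy, and within 28 days before C1D1, and must be repeated if it predates that therapy. Leave the intervals in exclusion 2 unchanged. This extends the principle 7.1 already applies to biopsied target lesions. The cost is one sentence in each place and a repeat scan for the few participants affected.

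2. **SAP.** In 5.1.1.1, 6.4.1.1 and 6.4.2.1 to 6.4.2.3, flag participants whose baseline scan predates their last prior anticancer therapy, and present iORR, ORR, iDCR and DCR with and without them. Scan dates and anticancer treatment in the 28 days before dosing are already collected (footnote k; SAP 6.2.5), so the cost is one derived flag and a repeated table. This is the part that can still be acted on after early termination.

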2 INTRODUCTION

In this study (0739-CL-0101), ASP0739 is indicated as a single agent and in combination with pembrolizumab in patients with advanced solid tumors known to express the tumor-associated antigen New York esophageal squamous cell carcinoma 1 (NY-ESO-1).

Details about ASP0739 are provided in the Investigator's Brochure.

Details about pembrolizumab are provided in the locally approved summary of product characteristics/package insert of this product.

2.1 Study Rationale

Cancer testis antigens (CTAs) have restricted expression in immune privileged organs (such as the testes and ovaries) and are silent in normal tissues. CTAs are stably expressed in many cancers and have high immunogenic potential [Gjerstorff et al, 2015]. In particular, NY-ESO-1 has high and frequent expression in malignant cancers [Jungbluth et al, 2001] and is able to elicit potent integrated natural humoral and cellular responses [Gnjatic et al, 2006]. ASP0739 has effects against NY-ESO-1 expressing tumors by inducing both natural killer cell activity (innate immunity) and NY-ESO-1-specific T cell dependent antitumor effects (adaptive immunity). Nonclinical studies were performed to demonstrate that both the innate and adaptive immune systems were activated by artificial Adjuvant Vector Cell (aAVC). In addition, nonclinical data suggest that ASP0739 is active in NY-ESO-1 expressing tumors as described in Section 4.1.1.3 of the Investigator's Brochure. A synergistic effect of ASP0739 with anti-programmed cell death protein 1 (anti-PD-1) antibodies was observed in a nonclinical setting as detailed in Section 4.1.1.5 of the Investigator's Brochure. Therefore, ASP0739 as monotherapy or in combination with anti-PD-1 antibodies may result in clinical benefit for solid tumors known to express NY-ESO-1.

2.2 Background

ASP0739 is an aAVC product composed of human embryonic kidney 293 (HEK293) cells that can be transfected with a lentiviral vector to express the tumor-associated antigens, in this case NY-ESO-1, intracellularly and the antigen-presenting molecule, cluster of differentiation 1d, on the cell surface. These genetically engineered cells are then loaded with α Galactosylceramide (α -GalCer), followed by X-ray irradiation to inhibit ASP0739 cell proliferation. Another aAVC compound, ASP7517, which uses the same platform and only differs in the intracellularly expressed antigen (Wilms' Tumor 1 [WT1] instead of NY-ESO-1) is currently being evaluated in an ongoing clinical study (7517-CL-0101). ASP7517 and ASP0739 are similar in their ability to activate innate and adaptive immunity and have similar nonclinical toxicology profiles.

NY-ESO-1 has been identified as a robust biomarker predicting clinical benefits with anti-PD-1 monotherapy and is useful for decision making in clinical settings [Oka et al, 2020]. NY-ESO-1 is considered to be the most immunogenic CTA and is a target for cancer vaccine strategies that utilize the immune system [Esfandiary & Ghafouri-Fard, 2015]. It has been reported that about 75% of patients with cancer express NY-ESO-1 at some stage of their

illness [Barrow et al, 2006]. Several studies on the utility of NY-ESO-1 as a surrogate marker of clinical response in multiple myeloma [Leutkens et al, 2014], gastric cancer [Fujiwara et al, 2013] and other malignancies have been conducted. Antibodies against NY-ESO-1 were observed during disease progression in multiple myeloma [Leutkens et al, 2014], as well as in gastric cancer, with the frequency of antibody positivity increasing during disease progression for patients with gastric cancer [Fujiwara et al, 2013]. NY-ESO-1 protein expression has been detected in invasive melanomas [Giavina-Bianchi et al, 2015] with a positivity rate of 32% to 45% [Bolli et al, 2005; Vaughn et al, 2004], esophageal squamous cell carcinoma (ESCC) [Ueda et al, 2018] with a positivity rate of about 32% [Akcakanat et al, 2004] and non-small cell lung cancer (NSCLC) [Wang et al, 2019] with 12% to 25% of tumors testing positive [Bolli et al, 2005; Jungbluth et al, 2001]. Studies have confirmed the high frequencies of NY-ESO-1 expression in MRCL and synovial sarcoma (SS), [Endo et al, 2015; Lai et al, 2012; Jungbluth et al, 2001]. NY-ESO-1 expression has also been noted as a sensitive and specific diagnostic biomarker in myxoid/round cell liposarcoma (MRCL) [Hemminger et al, 2013; Pollack et al, 2012]. Early data have shown that NY-ESO-1 is a valid target to generate clinical response via immunological activation.

A detailed description of the chemistry, pharmacology, efficacy and safety of ASP0739 is provided in the Investigator's Brochure.

2.2.1 Synovial Sarcoma and Myxoid/Round Cell Liposarcoma

In the US, 13130 new patients (7470 males and 5660 females) are forecasted to be diagnosed with soft tissue sarcomas and 5350 patients are expected to die of the disease in 2020 [American Cancer Society, 2020]. For patients diagnosed with soft tissue sarcomas between 2009 and 2015, based on combined Surveillance, Epidemiology and End Results stages, the 5-year survival rate was 65% [American Cancer Society, 2020]. SS is an uncommon malignant tumor of the tissue around the joints with the most common locations being the extremities with distant pulmonary metastases developing in most patients after primary tumor surgery [Zhang et al, 2014]. SS accounts for about 5% to 10% of soft tissue tumors [Fisher, 1998]. About 50% of patients die within 10 years of diagnosis even with treatment [Terry et al, 2005]. MRCL is typically found in the lower extremities [National Institutes of Health, 2016]. Prognosis is better for patients with a low grade MRCL with a small percentage of round cells (5-year survival rate of 92%) whereas a greater percentage of round cells (5% or higher) is associated with a much poorer prognosis and a 5-year survival rate of 74% [Orphanet, 2013]. A systematic review of sarcoma survival rates indicated that 5-year survival rates for all patients with metastatic sarcoma were 20% to 25% for bone, and for soft tissue sarcoma 13% to 15% [Treasure et al, 2012]. About 88% of tumors in MRCL and 76% to 80% of tumors in SS express NY-ESO-1 [Endo et al, 2015; Lai et al, 2012; Jungbluth et al, 2001].

